Screening: Once the patient signs the consent form, a screening period of up to two weeks will initiate to determine the patient's eligibility for the study, prior to entering the randomization phase. Only eligible patients will enter the randomization phase.

Randomized Phase: Monthly infusions (of either B or P) will start at week 0 and continue every four weeks until week 36 (10 months) for the “randomized” phase of the study. In addition, there will be a “loading dose” at week 2 (per drug [IND] specifications). The loading dose will consist of either Belimumab or Placebo (saline) in the B or P treatment arms, respectively.

Open Label Phase: Monthly infusions (of B) will start at week 40 and continue every four weeks until week 64 (6 months) for the “open-label” phase of the study.

A comprehensive evaluation of the patient (Physical exam and history, vital signs, AEs, CBC and metabolic panel, GGT, myoglobin, pregnancy test, urinalysis, ESR, CRP, CPK, immunoglobulins, muscle and health evaluations, physician global assessment, patient self-assessments, serum level sampling) will be conducted at weeks 0, 8, 16, 24, 32, 39-40, 52, 64. A less comprehensive set of evaluations (vital signs, AEs, CBC and metabolic panel, GGT, pregnancy test) will be conducted at weeks 2, 4, 12, 20, 28, 36, 40, 44, 48, 56, 60. A detailed schedule of visits and procedures is outlined in appendix A.

A telephone follow-up conversation will also be conducted at weeks 72 and 84.

Optional Exploratory Studies

Blood based biomarker assessments and blood based RNA assessments will be performed on stored samples for consenting patients at Northwell Health only. See Appendix A (schedule of events).

b. Randomization:

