The Biostatistics Unit at the Feinstein Institute for Medical Research [BU-FIMR] will develop a web based randomization plan for the study. A randomization schema will be generated by the BU-FIMR for each participating site using the method of permuted blocks. Subjects will be randomly assigned in a 1:1 ratio to either Belimumab or Placebo, according to two stratification variables, namely, disease type (Polymyositis or Dermatomyositis) and disease severity (severe or less severe). The Biostatistics Randomization Management System (BRMS) is a secure, HIPAA-compliant, web-based application that allows investigators to randomize subjects into randomized clinical trials (RCTs) using their personal computer. The BRMS allows for multi-center, stratified, and single/double blinded RCTs, using permuted blocks. Randomization notifications are automatically sent to the PI and other authorized personnel. Using BRMS is a good way to maintain compliance in RCTs.

c. Stratification:

Randomization will be according to the two important stratification variables: disease type (Polymyositis vs. Dermatomyositis) and disease severity (severe vs less severe) and will occur at week 0 (first infusion). The number of immunosuppressive agents used by the patient over the last year (corticosteroids are not included) will be used as a surrogate of disease activity: one or less IS agent over last year versus more than 1 IS agent over last year.

d. Blinding:

This is a double-blind study; both the investigator and the patient will be blinded to the treatment assignment in the randomized phase of the trial. At the end of the 40 week randomized treatment phase all subjects will start the 20 week open label phase and therefore the drug will be dispensed in the unblinded fashion.

For each study site, there will be a designated unblinded research coordinator (URC) and a blinded research coordinator (BRC). The URC will be responsible for obtaining randomization assignments from the BU-FIMR and will oversee the preparation of infusions prior to drug administration. The BRC will be responsible for coordinating patient visits and administration or the infusion (infusion will be masked and not identifiable through any physical characteristics such as color or consistency, as the drug is of a powder form mixed in saline solution).

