2. Elevation of at least one muscle enzyme (creatinine kinase [CK]; myoglobin; alanine aminotransferase [ALT]; or aspartate aminotransferase [AST]) to a minimum level of 1.3 times the upper limit of normal.
3. Physician Global Assessment ≥ 2.0 cm using a visual analogue scale (VAS) 10.0 cm in length.
4. Patient Global Assessment ≥ 2.0 cm using a visual analogue scale (VAS) 10.0 cm in length.
5. Global extra muscular disease activity score ≥ 1.0 cm using a visual analogue scale (VAS) 10.0 cm in length. This score is based on the investigator's composite assessment of disease activity of the constitutional, cutaneous, skeletal, gastrointestinal, pulmonary and cardiac scales on the Myositis Disease Activity Assessment Tool (MDAAT).
6. HAQ disability index with a minimum value of 0.25.

The patient will be required to meet an MMT 8 score of $\leq 125/150$ as a major CSM criterion and at least 2 other CSM criteria to classify as an active disease.

In addition, for patients with ≥ 7 years of IIM, muscle biopsy or muscle MRI within 4 months prior to enrollment will be required to document active myositis to avoid enrolling patients with

significant index of damage/ muscle atrophy. This is not applicable to DM patients with a cutaneous VAS score of >3 cm on a 10 cm VAS scale (MDAAT).

Response rate: The response rate will be assessed by the percentage of patients meeting the definition of improvement (DOI). DOI is based on the definition of improvement developed by the International Myositis Assessment and Clinical Studies Group utilizing 6 core set measures.

DOI: DOI is defined as $\geq 20\%$ improvement in any 3 of the CSM, with no more than 2 CSM worsening by $\geq 25\%$ (excluding MMT)¹¹.

Definition of Worsening (DOW): Determination of worsening of the disease activity will be based on the definition of worsening (DOW) criteria developed by the International Myositis Assessment and Clinical Studies Group (IMACS) utilizing 6 core set measures¹¹:

1. worsening of Manual Muscle testing by $\geq 20\%$ and or Physician Global worsening of ≥ 2 cm on a 10 cm VAS or
2. Global extra muscular organ disease activity worsening by ≥ 2 cm on a 10 cm VAS on MDDAT, or
3. 3 of 6 CSM worse by $\geq 30\%$

Disease Flare: IIM Disease Flare is recorded when the patient:

1. reaches DOW;
2. new start or dose increase of corticosteroid or immunosuppressive agent for treatment of IIM after study week 8;

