3. an increased dose of corticosteroid before study week 8 and did not return to $<25\%$ above the baseline dose by week 12.

Endpoints:

1. **Primary Endpoint:**
 - a. Response rate at 40 weeks defined as percentage of patients meeting definition of improvement (DOI) in IIM patients treated with belimumab and standard therapy compared to the percentage of patients meeting DOI treated with placebo and standard therapy.
2. **Secondary Endpoints:**
 - a) Incidence of flares: flare rates during 40 weeks randomization period in patients with IIM treated with belimumab and patients treated with placebo and at week 64 in each group.
 - b) Time to achieve initial improvement defined as the time to reaching DOI.
 - c) Duration of improvement; quantified as the time from achieving improvement to the time of worsening or a disease flare. (Time from 1st DOI to 1st DOW or disease flare event). This will be based on the subset of subjects who achieve improvement.
 - d) Percent change in muscle enzyme levels (CPK and myoglobin) from baseline to week 40 and 64 in each respective group
 1. $<20\%$ reduction: no response
 2. 20-70% reduction: partial response
 3. $>70\%$ reduction: complete response
 - e) Percent change in manual muscle assessment (MMT-8) from baseline to week 40 and week 64 in each respective group.

- 1. <20% reduction: no response
- 2. 20-70% reduction: partial response
- 3. >70% reduction: complete response
- f) Percent change in prednisone dose from baseline to week 40 and week 64 in each respective group
- g) Proportion of subjects, among those on steroids at baseline, able to reduce the prednisone dose to ≤ 5 mg daily at week 40 and week 64 in each respective group.
- h) Flare rate in placebo group during the 40 week randomized treatment phase as compared to that group in the 20 week open label phase.
- i) Serious adverse event and adverse event rates
- j) Changes in B cell populations from baseline to week 40 and week 64
- k) Changes in autoantibody titers from baseline to week 40 and week 64
- l) Changes in immunoglobulin concentrations from baseline to week 40 and week 64

Inclusion Criteria:

Subjects enrolled in the study must meet the following inclusion criteria:

- 1) Adults ≥ 18 years of age
- 2) Have a diagnosis of:
 - a. definite or probable dermatomyositis (DM) by modified Bohan & Peter criteria or

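### Secondary endpoint h calls the open-label phase 20 weeks long although the schedule runs to week 64; read literally, it loses one of only two open-label visits at which worsening can be scored

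*Combined protocol and SAP*

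**What the plan says.** Secondary endpoint h compares the placebo group with itself: "Flare rate in placebo group during the 40 week randomized treatment phase as compared to that group in the 20 week open label phase". The Blinding paragraph of Study Design gives the same length, saying that when the 40-week randomized phase ends "all subjects will start the 20 week open label phase".

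The Open Label Phase paragraph of Study Procedures and Schedule gives a longer phase: "Monthly infusions (of B) will start at week 40 and continue every four weeks until week 64 (6 months". The same section says the comprehensive evaluation "will be conducted at weeks 0, 8, 16, 24, 32, 39-40, 52, 64", and the reduced one "will be conducted at weeks 2, 4, 12, 20, 28, 36, 40, 44, 48, 56, 60". Week 64 is on the first list and week 60 on the second. Study Procedures & Assessments agrees: after week 40, MMT-8, physician global, MDAAT, HAQ and patient global are scheduled only at weeks 52 and 64.

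Under Definitions, a flare is recorded when a patient reaches DOW, or on a treatment change such as "new start or dose increase of corticosteroid or immunosuppressive agent for treatment of IIM after study week 8". DOW requires worsening in muscle testing or physician global, in the extramuscular activity score, or in at least three of the six core set measures.

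Secondary endpoint a reports flares during the randomized period for belimumab and for "patients treated with placebo and at week 64 in each group". Endpoints d, e, f, g, j, k and l also use week 64 as their open-label time point.

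**The concern.** Endpoint h is the only listed comparison of the placebo group's flare rate before and after it starts belimumab. If its open-label window closes at week 60, the last visit inside it at which DOW can be scored is week 52. Patients then contribute follow-up from week 52 to week 60 during which a DOW flare cannot be found at any scheduled visit. The randomized phase has no such stretch, because week 40 is itself a core-set visit. DOW flares would therefore look rarer on open-label belimumab even if the drug did nothing.

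Statistical Methods assigns h no window, denominator or test, so nothing elsewhere in the plan resolves the conflict. The choice would be left to the analyst, possibly after the open-label data are known.

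**Working it through.** **1. Where 20 weeks could come from.**
- From the week 40 start: 40 + 20 = week 60. This is also the span from first to last of six infusions (weeks 40, 44, 48, 52, 56, 60). Counted that way, the randomized phase would be 36 weeks (infusions at weeks 0 to 36), but the plan calls it 40, which is 36 + 4. The same convention with a last infusion at week 60 gives 60 + 4 = week 64, or 24 weeks.
- Weeks 44 to 64 also span 20 weeks, but both the Blinding and Open Label Phase paragraphs start the phase at week 40.
- The stated schedule gives 64 − 40 = 24 weeks, not 20.

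**2. Can DOW be scored at week 60?** Of the six core set measures, only muscle enzymes can be available then: ALT and AST through the metabolic panel, plus CPK and myoglobin if the instruction to draw laboratory tests at all visits is followed. That is one of six. The first two routes to DOW lack their measures and the third needs three. DOW cannot be scored.

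**3. DOW assessments in each window.**

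| Window | DOW visits (weeks) | Number | Weeks after last DOW visit | Average spacing |
|---|---|---|---|---|
| Randomized, 0 to 40 | 8, 16, 24, 32, 40 | 5 | 0 of 40 | 40/5 = 8 weeks |
| Open label, 40 to 60 | 52 | 1 | 60 − 52 = 8 of 20 (40%) | one visit only |
| Open label, 40 to 64 | 52, 64 | 2 | 0 of 24 | 24/2 = 12 weeks |

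**4. Size under no drug effect (illustration).** The documents give no DOW-flare risk, so take a 40-week risk p of 10% to 50%. Assume the same constant hazard in both phases, L = −ln(1 − p)/40; worsening that lasts to the next core-set visit; no unscheduled core-set assessment; and all 15 placebo patients completing and at risk in both phases. A flare is found at the next core-set visit. The rate is the probability that a flare is found divided by expected weeks to detection or window end.

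For p = 10%, L = 0.002634:
- Randomized: found 0.100; expected weeks 8 × (1 + e^(−8L) + e^(−16L) + e^(−24L) + e^(−32L)) = 38.37; rate 0.002606 per week.
- Open label to week 60: found 1 − e^(−12L) = 0.0311; expected weeks 12 × 0.0311 + 20 × 0.9689 = 19.75; rate 0.001575. Ratio to randomized: 0.604.
- Open label to week 64: found 1 − e^(−24L) = 0.0613; expected weeks 12 × 0.0311 + 24 × 0.9689 = 23.63; rate 0.002593. Ratio: 0.995.

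| Assumed p | Rate ratio, to week 60 | Rate ratio, to week 64 | Found among 15, to week 60 | Found among 15, to week 64 |
|---|---|---|---|---|
| 10% | 0.604 | 0.995 | 0.47 | 0.92 |
| 20% | 0.609 | 0.989 | 0.97 | 1.88 |
| 35% | 0.617 | 0.979 | 1.82 | 3.42 |
| 50% | 0.627 | 0.967 | 2.82 | 5.10 |

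**5. The same comparison with simple proportions.** If h is reported as the proportion of patients with any flare, the null ratio is (1 − (1 − p)^(12/40))/p to week 60, which is 0.31 to 0.38 for p = 10% to 50%. To week 64 it is (1 − (1 − p)^(24/40))/p, which is 0.61 to 0.68. Correcting the window helps, but proportions still set 24 weeks of follow-up against 40.

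**The case against.** The strongest reply is that no sentence says h ends at week 60. That is only 40 + 20. Endpoint h names a phase, the paragraph headed Open Label Phase runs to week 64, and the other endpoints stop there, so an analyst could take 20 weeks as a loose label and keep the week 64 visit. This stands as far as it goes. A reader might infer that the week 64 assessment is certainly lost to h, or that the sponsor chose to exclude it; the documents support neither. But the Blinding paragraph fixes the start at week 40 and repeats the 20 weeks, so the literal reading is available and nothing overrules it.

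Three further points stand. Treatment-change flares need no core-set visit, so those up to week 60 are caught under either reading. Endpoint a already reports flares at week 64, so the week 64 data are collected and used however h is read. And the rate ratios near 1 depend on a person-time rate, whereas the first flare analysis in Statistical Methods is the proportion with any flare, with an incidence density ratio as an optional addition. A reader might infer that correcting the window alone makes the phases comparable; step 5 shows that it does not.

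A reader might also infer that the infusion sentence needs rewording, since 20 weeks and six months both suggest a last dose at week 60. The dosing row of Appendix A cannot be aligned in the available text. Whether week 64 is dosed is a separate question and does not affect h.

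**Conclusion.** The 20-week figure in endpoint h and in the Blinding paragraph conflicts with the schedule: wrong as written, but minor. What is established is an ambiguous window. On its literal reading, h has one scheduled DOW assessment rather than two and 8 of 20 weeks unassessed for DOW, which biases the before-and-after comparison towards belimumab. Under the stated assumptions, the DOW-flare rate would appear about 37% to 40% lower with no drug effect. That size rests on a constant hazard, worsening that persists to the next visit and an assumed risk of 10% to 50%; the visit counts rest on the documents alone. The illustration covers DOW flares only, so the distortion in all flares combined would be diluted by treatment-change flares, in a proportion the documents do not give.

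The consequence is confined to one uncontrolled within-group comparison with no assigned test. Endpoint a and the week 40 primary endpoint are unaffected.

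**What to change.** In secondary endpoint h and in the Blinding paragraph, replace the 20-week description with weeks 40 to 64 (24 weeks), so that the week 64 core-set assessment counts in h. Changing the schedule to end at week 60 instead would make the text agree but keep the gap.

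State that h will be reported as flares per unit of patient-time in each phase, because phases of 40 and 24 weeks cannot be compared fairly as simple proportions. Add that DOW visits remain 12 weeks apart in open label against 8 in the randomized phase, so worsening that resolves between visits is more likely to be missed in open label.

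The cost is a wording change in two places plus one or two sentences on the analysis of h. No visit, test or data item is added, since the week 64 core-set visit is already scheduled. The infusion schedule needs no change for this purpose.

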Adverse Event and Serious Adverse Event Reporting:

The investigator or site staffs are responsible for detecting, documenting and reporting events that meet the definition of an AE or SAE.

- All AEs must be reported to the coordinating site.
- All SAEs must be reported to the coordinating site and local IRB within 24 hours. The coordinating site will report all SAEs to the coordinating site's IRB, the sponsor and the FDA.

All AEs and SAEs must be reported on an Adverse Event/Serious Adverse Event case report form. The study investigator is responsible for noting the relationship of the event to the study drug, the severity of the drug (criteria for grading toxicity will be based on NCI's Common Terminology Criteria for Adverse Events version 4.03), the actions taken with the investigational product, and any other medications used to treat the adverse event or serious adverse event.

Time Period and Frequency of Detecting AEs and SAEs:

The investigator or site staffs are responsible for detecting, documenting and reporting events that meet the definition of an AE or SAE. AEs will be collected from the start of the study treatment until the end of the study. SAEs will be collected from the start of the study treatment until the end of the study. All SAEs will be reported to the coordinating site, sponsor and IRB within 24 hours.

NOTE: Any SAEs assessed as **related** to study participation (e.g. study treatment, protocol-mandated procedures, invasive tests, or change in existing therapy) or related to a GSK concomitant medication, will be recorded from the time a subject consents to participate in the study up to and including any follow up contact.

Study Procedures & Assessments:

The following assessments will occur throughout the study (see Appendix A for schedule of events):

- Informed Consent and Inclusion/Exclusion Criteria will be assessed at the screening visit. After a subject signs the informed consent they will enter the screening period (≤ 2 weeks) and have eligibility determined prior to Day 0.

Laboratory assessments:

- a. CBC, Comprehensive metabolic, GGT, ESR, CRP, CPK, serum myoglobin, immunoglobulins, urinalysis and urine pregnancy test will be collected at screening.
- b. CBC, Comprehensive metabolic, GGT, ESR, CRP, CPK, serum myoglobin, immunoglobulins and urinalysis **collected within 2 weeks prior to screening can be used** for eligibility determination.

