- c. Testing for latent TB is a standard of care for patients on immunosuppressive therapy and results will be obtained **from their medical record**. If no TB history is found for these patients, a Quantiferon Gold or PPD test will be performed prior to Day 0 as part of **standard of care**.
- d. Hepatitis status will be obtained from patients' **medical records**. If unavailable, testing will be done as part of **standard of care** during the screening period.
- Vital signs will be assessed prior to infusion and after the infusion at every visit.
- Adverse events assessed at every visit. Criteria for grading toxicity will be based on NCI's Common Terminology Criteria for Adverse Events version 4.03. (Adverse Events/Serious Adverse Events (CTCAE Version 4.03)
- A Physical Exam will be performed by the Investigator at Screening, Day 0, Week 8, 16, 24, 32, 40, 52, & 64.
- Urine Pregnancy testing for WOCBP will be conducted at each study visit and 16 weeks after last dose. Urine pregnancy tests must be completed < 7 days prior to the first dose and prior to each IP administration, but not more than once a month. In the event that the urine pregnancy test is indeterminate, a serum pregnancy test will be done.
- Laboratory tests: CBC, Comprehensive metabolic, GGT, ESR, CRP, CPK, myoglobin and urinalysis will be collected at every study visit and follow up week 64.
- An immunoglobulin panel will be collected and assessed at: Screening, Week 40, & 64. Under special circumstances monthly IgG monitoring may be required (see Section: Study Design, part f) and will be performed as part of standard of care.
- Flow Cytometry and RNA-seq are collected at: Day 0, Week 8, 40, Week 48, & Week 60 or 64.
- Cytokine levels (and optional research Northwell only) will be measured at: Day 0, Week 40, & Week 60 or Week 64.
- Patients should be clinically assessed for suicidal ideation and/or behaviour at each study visit using the Columbia Suicide Severity Scale (C-SSRS)
- The Investigator will complete a Physician Global Assessment (PGA, a VAS scale of 10cm), Manual Muscle Test-8 (MMT-8), & Myositis Disease Activity Assessment Tool (MDAAT) at Screening, Day 0, Week 8, 16, 24, 32, 40, 52, & 64
- The Investigator will complete a Muscle Damage Index (MDI) assessment at Screening, Week 40 and Week 64
- Health Assessment Questionnaire (HAQ) and Patient Global Assessment (PGA, a VAS scale of 10cm) will be completed by subjects at Screening, Day 0, Week 8, 16, 24, 32, 40, 52, & 64

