The Biostatistics Randomization Management System (BRMS) is a secure, HIPAA-compliant, web-based application that allows investigators to randomize subjects into randomized clinical trials (RCTs) using their personal computer. The BRMS allows for multi-center, stratified, and single/double blinded RCTs, using permuted blocks. Randomization notifications are automatically sent to the PI and other authorized personnel. Using BRMS is a good way to maintain compliance in RCTs.

Statistical Considerations

SPECIFIC STATISTICAL AIMS

The primary objective of the study is to compare subjects in the Belimumab group and subjects in the placebo group with respect to response (improvement) at week 40.

The specific aims of the study are to compare the two treatment arms (Belimumab vs. Placebo [P vs. B]), during the 40-week randomized phase of the study, with respect to the following:

1. Response at week 40.
2. Flare rates during the 40-week treatment period.
3. Time-to-achieve (initial) improvement during the 40-week randomized phase of the study
4. Duration of improvement during the 40-week randomized phase of the study, among those who achieved improvement (this is essentially a time-to-flare/relapse analysis from the time that you achieved improvement)
5. Change in muscle enzyme levels (CPK, myoglobin) from baseline to week 40
6. Change in MMT-8 from baseline to week 40
7. Change in prednisone dose from baseline to week 40

8. Proportion of subjects able to reduce prednisone dose to ≤ 5 mg at week 40
9. Change in B cell populations, immunoglobulin levels and BLys levels from baseline to week 40.
10. Change in autoantibody titers from baseline to week 40.
11. Rates of SAEs and AEs experienced

STATISTICAL METHODS

All subjects will be analyzed according to the intention-to-treat [ITT] principle. A subject will be considered evaluable and will be included in the intention-to-treat analysis if he/she received at least the first five of the planned infusions during the randomized phase of the study. Subjects who do not get the first five infusions will be considered ‘drop-outs’. It should be noted that the study protocol calls for patients remaining on their treatment assignment. However, adjustments in dosages of medications used in their ‘standard care’ are permitted during the first 8 weeks. Analyses that take into account the actual treatment received (e.g. accounting for compliance, etc.) will be carried out as a secondary analysis (per protocol [PP] analysis).

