
1. For specific aim 1, the two treatment arms [B vs. P] will be compared with respect to the proportion of subjects who respond to treatment at 40 weeks (improvement according to definition), using either a chi-square test or Fisher’s exact test, as appropriate.
2. For specific aim 2, either a chi-square test or Fisher’s exact test, as appropriate, will be conducted to compare the proportion of subjects who had any flares during the 40-week randomized phase. For this analysis, each subject will be categorized at the end of 40 weeks as having had one or more flares or not having had any flares. In addition, we can also examine the total number of days that a subject had a specific flare during the course of the 40-week treatment, and compare the two treatment arms using the ‘Incidence density ratio’ method.
3. For specific aim 3, standard methods for survival analysis will be carried out. The Kaplan-Meier (KM) product limit method will be used to estimate overall “time-to-achieve (initial) response/improvement”. Ninety-five percent confidence intervals will be calculated using Greenwood’s formula for computing the standard error. Subjects who have not achieved improvement as of week 40 will be considered ‘censored’ for the event (event=improvement/response).
4. For specific aim 4, similar methods as indicated for specific aim 3 will be conducted. The analysis for this aim will be limited to the subset of subjects in each treatment arm who show improvement at anytime during the randomized phase of the trial. A subject who has not flared/worsened/relapsed as of week 40 will be considered ‘censored’ for the event (event=flare/relapse).
5. For specific aims 5, 6, 7, 9 and 10, each of the outcome variables of interest (uncensored continuous or categorical) will be analyzed separately, using a mixed model approach to repeated measures analysis of variance (MMRMANOVA) with the main effects of treatment arm (B vs. P), Disease type (PM vs DM), Disease Severity (Severe vs. Less Severe) and time (baseline vs. 40 weeks). If feasible, statistical interactions between

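### Change in autoantibody titre is a secondary endpoint and a specific aim, but the protocol schedules no titre at any visit

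*Combined protocol and SAP*

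**What the plan says.** The Endpoints section lists, as secondary endpoint k, "Changes in autoantibody titers from baseline to week 40 and week 64". Specific Statistical Aims, aim 10, repeats it as a comparison of the arms in the randomised phase: "Change in autoantibody titers from baseline to week 40". The aim stops at week 40; the endpoint goes on to week 64. Statistical Methods, item 5, assigns the analysis: "For specific aims 5, 6, 7, 9 and 10, each of the outcome variables of interest (uncensored continuous or categorical) will be analyzed separately", by a mixed model with treatment arm, disease type, disease severity and time (baseline against week 40).

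Collection is described in Study Procedures & Assessments and in Appendix A. At screening, "CBC, Comprehensive metabolic, GGT, ESR, CRP, CPK, serum myoglobin, immunoglobulins, urinalysis and urine pregnancy test will be collected at screening". During the study, "CBC, Comprehensive metabolic, GGT, ESR, CRP, CPK, myoglobin and urinalysis will be collected at every study visit and follow up week 64". For immunoglobulins, "An immunoglobulin panel will be collected and assessed at: Screening, Week 40, & 64". Flow cytometry, RNA-seq and cytokines have their own dates. Under Optional Exploratory Studies, blood-based biomarker and RNA work "will be performed on stored samples for consenting patients at Northwell Health only".

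Autoantibodies otherwise appear in the Definitions and in inclusion criteria 2 and 3, where positivity is needed for entry, and in Appendix C, where ANA, anti-smooth muscle and anti-LKM antibodies are tested after a liver event that meets the bilirubin or INR criteria.

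**The concern.** An endpoint of change needs a measurement at each end of the interval. A site that followed the assessment text and Appendix A exactly would order no autoantibody titre at Day 0, week 40 or week 64, and the statistician would then have nothing to put into the model named for aim 10.

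The baseline matters most. A later visit can sometimes be made good with a late sample, but a pre-treatment titre cannot be obtained once the first infusion has been given. If sites noticed the gap and improvised, the trial would hold titres from different laboratories and assays, taken at different times, in a study of only 30 patients.

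**Working it through.** There is no figure in the plan to reproduce. The check sets what the endpoint needs against every place where the protocol says what is collected.

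**What is needed.** Endpoint k needs a titre at baseline, week 40 and week 64. Aim 10 needs the first two.

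**What is scheduled.**

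| Place in the protocol | Nearest item | Autoantibody titre named? |
|---|---|---|
| Study Procedures and Schedule (visit summary) | Serum level sampling, not defined, at weeks 0, 8, 16, 24, 32, 39-40, 52 and 64 | No |
| Optional Exploratory Studies | Stored-sample biomarker work, optional, one centre | No |
| Study Procedures & Assessments, screening laboratory list | Immunoglobulins | No |
| Study Procedures & Assessments, per-visit list | Immunoglobulins, flow cytometry, RNA-seq, cytokines | No |
| Appendix A, row labels and notes | Total IgG, IgA and IgM | No |
| Appendix C, liver event follow-up | ANA and two other antibodies, after an event only | Not a scheduled assessment |

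The result for Appendix A does not depend on which cells are ticked, because no row carries such a label. The prose lists agree with it independently.

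**Comparison with the neighbouring endpoints.** Endpoint j (B cell populations) has flow cytometry at Day 0, week 40 and week 60 or 64. Endpoint l (immunoglobulins) has a panel at screening, week 40 and week 64. Of these three adjacent biomarker endpoints, only k has no assay behind it. That looks like an omission rather than a habit of leaving assays out of the schedule.

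**Could the eligibility result serve as baseline?** Inclusion criterion 3 accepts ANA at 1:80 or above, RNP, SSA/SSB, or any of ten listed myositis-specific antibodies. The ANA route implies a titre on record; the other routes require only a positive result. No time window, assay or laboratory is given, and the screening laboratory list contains no autoantibody test, so the result may be historical. Even a usable baseline would leave weeks 40 and 64 empty.

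**Count.** Scheduled titres per patient: 0 at baseline, 0 at week 40, 0 at week 64.

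**Size of the remedy.** With 30 patients and all visits completed:
- endpoint k: 30 x 3 = 90 samples;
- of these, aim 10 uses 30 x 2 = 60.

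The number of assays is 90 x a, where a is the average number of antibodies measured per sample. The documents do not give a, so 90 assays is right only if a = 1.

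**A second gap.** The plan does not say which antibody's titre is the outcome, by what assay, or on what scale. Patients may enter on different antibodies, so raw titres from different patients are not one variable. Adding a bare titre row to the schedule would not be enough to make the mixed model workable.

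**The case against.** The strongest reply is that blood for this purpose may already be planned. The visit summary schedules serum level sampling for all patients at weeks that include 0, 39-40 and 64, which are the three time points of endpoint k. Cytokine blood is scheduled at Day 0, week 40 and week 60 or 64 and has an Appendix A row separate from the optional research limited to one centre. A laboratory manual outside these documents could also specify the assay. This part stands: the documents do not show that titres would never be measured. But the serum item is undefined, has no Appendix A row and is not linked to autoantibodies, and nothing provides for keeping cytokine serum or testing it for them.

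A reader might infer that only consenting patients at one centre could ever be assayed, or that most sites would have no data. The documents do not support either. The one-centre limit applies to the optional work, cytokine blood is not confined to it, and neither the number of sites nor the patients per site is given. Nor is it right that eligibility never involves a titre, since the ANA criterion is a titre threshold.

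It is also fair to say that k is one of twelve secondary endpoints, and that objective d names B cell populations and cytokine levels but not autoantibodies. That limits the importance of the gap. It does not close it.

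**Conclusion.** The point holds as an inconsistency between endpoint and schedule. From the data the protocol schedules, endpoint k and aim 10 cannot be analysed: the planned titres are zero at all three time points for all 30 patients. The conclusion rests on two assumptions: that the assessment text and Appendix A are the complete list of collections, and that the undefined serum item does not mean autoantibody titres. If the sponsor can show that it does, the defect narrows to a missing definition of sample, antibody and assay, which still has to be supplied.

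A reader might go further and infer that the trial's main conclusion is at risk. It is not. The primary comparison of response at week 40 and the sample size use no autoantibody data. The change is still worth making before enrolment, because the baseline loss is permanent and the remedy is small.

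**What to change.** Either schedule and define the measurement, or remove it.

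1. **Schedule.** Add an autoantibody row to Appendix A and a matching line to Study Procedures & Assessments for Day 0 (before the infusion), week 40 and week 64, at all sites, as an aliquot from blood already drawn at those visits. Say what serum level sampling means, or delete the term.
2. **Define.** State that the titre followed is that of each patient's baseline-positive antibody or antibodies, measured with one assay per antibody in a single batch. Give a rule for patients positive for more than one.
3. **Analyse.** In Statistical Methods, item 5, state that the outcome for aim 10 is within-patient change on a log scale, so that patients with different antibodies are compared on relative change.
4. **Or delete** endpoint k and aim 10, and take aim 10 out of item 5.

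The cost of keeping the endpoint is a schedule entry, storage of about 90 aliquots if all 30 patients complete, and a modest assay bill that depends on how many antibodies are tested. No extra visit is needed. Deleting it costs nothing beyond the loss of one secondary biomarker endpoint.
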